Evidence supports that AD neurodegenerative changes likely begin decades before clinically-apparent disease. The NIA-Alzheimer's Association (AA)-sponsored workgroup defined research criteria for the preclinical stages of AD and identified factors that best predict risk of progression from "normal" cognition to mild cognitive impairment (MCI) and AD. Our investigative team at the NIH-funded, jointly-sponsored University of Wisconsin (UW)/ Madison VA Wisconsin Alzheimer's Disease Research Center (ADRC) has focused our studies on early identification and treatment of such preclinical, high-risk individuals - in particular, asymptomatic middle-aged adults with parental history of AD. While previous studies have demonstrated that having a firstdegree relative with AD increases the risk of developing AD, independent of the risk conveyed through the genetic risk factor apolipoprotein Ε ε4 (APOE4) allele, more recent research supports that biomarker elevations, but not APOE or parental history status, are associated with risk of cognitive decline in cognitively unimpaired adults. 1 Our Wisconsin ADRC investigators have found that asymptomatic middle-aged adults with parental history of AD show early neurobiological changes on CSF biomarkers, MRI biomarkers including measures of regional cerebral blood flow (rCBF), and cognitive biomarkers for AD while demonstrating normal global cognitive and clinical function. In a group of 218 cognitively healthy adults ages 40-65 years with parental history of AD in our Wisconsin ADRC-related studies, we found that 129 (60%) are either carriers of the APOE4 allele or have CSF β-amyloid-42 (Aβ42) or tau biomarker levels suggesting preclinical disease (preliminary data, unpublished). Thus, these high-risk individuals are ideal to study in that they are clinically asymptomatic, yet have neurobiological evidence supporting preclinical AD-related changes in their brains. For the proposed clinical trial, we will focus on cognitively healthy Veterans ages 50-75 years with or without parental history of AD. Participants will have Veteranspecific risk factors related to increased prevalence of atherogenic vascular risk profiles, TBI, PTSD, and depression. In addition, we will gather information on their parental history of AD to account for potential risk variation given the conflicting findings on the importance of parental history of AD in the development of this common form of dementia.

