# C) RESEARCH DESIGN AND METHODS

#### **Trial Design Summary**

The proposed proof-of-concept study will use an 18-month randomized, placebo-controlled, double-blind, parallel-group clinical trial design to investigate the effects of IPE (available as Vascepa® in the United States) on rCBF, CSF AD biomarkers, and cognition in 150 cognitively-healthy Veterans ages 50-75 years at increased risk for AD due to their Veteran-related risk factors including high vascular risk profiles, TBI, and PTSD. The primary aim of the trial (**Specific Aim 1**) is to assess whether IPE increases 18-month rCBF in a statistically-defined region of interest (sROI) in a population of middle-aged veterans compared to placebo. Key secondary aims within this proof-of-concept pilot RCT are: (**Specific Aim 2**) to assess whether IPE decreases CSF A $\beta$ 42; and (**Specific Aim 3**) to assess whether IPE improves cognitive performance on the ADCS-PACC battery compared to placebo. Data collected within this clinical trial will also allow exploratory analyses of the effects of IPE on measures of axonal and neuronal health, including CSF biomarkers (total tau, phosphorylated tau [p-tau], neurofilament light [NFL] protein, soluble amyloid precursor protein  $\alpha$  and  $\beta$  [sAPP- $\alpha$  and sAPP- $\beta$ ], monocyte chemotactic protein 1 [MCP1], YKL-40, and other CSF measures) and neuroimaging biomarkers (diffusion

weighted imaging, volumetric changes, 4D flow measures, and white matter hyperintensity measures among others). In addition, data collection from this trial will allow for exploration of the impact of previous TBI and/or PTSD on response to therapy. We hypothesize that in this population, IPE will beneficially affect mechanisms central to AD pathology by: 1) increasing rCBF within the sROI; 2) reducing CSF A $\beta$ 42; and that these neurobiological changes will be associated with 3) an increased ADCS-PACC cognitive composite score. While recognizing that the proposed trial is not addressing all potential effects of IPE, such as changes in measures of inflammation or oxidative stress, we will store neuroimages and blood and CSF samples for future analyses of other potential mechanisms.

Table 2. Study Design

VA BRAVE-EPA STUDY	Visit Number/Month (+/- 8 weeks)								
VA DRAVE-LPA STODI	Pre-	Bse	V2	V3	V4	V5	V6	V7	Final (Or
	Study	V1	M1	M3*	M6*	M9	M12*	M15*	Early
	V0	M0							Termination)
	M-1								Visit V8 M18
Eligibility review	Х								

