To test this hypothesis, we will enroll 150 cognitively healthy male and female Veterans and randomize them in a 1:1 ratio to IPE 4 g daily or matching placebo. All participants will undergo informed consent and will be screened for eligibility via a pre-study screening visit (Table 2). At baseline and months 9 and 18, all participants will undergo MRI, lumbar puncture (LP) for CSF collection, a blood draw, cognitive testing, vascular risk assessment, and will complete questionnaires including a food frequency questionnaire (FFQ) targeting omega-3 fatty acid intake and screening questions assessing prior combat and non-combat deployment, TBI, PTSD, and related sequelae. At months 1, 3, 6, 12, and 15, participants will have an assessment of medical/medication changes and potential side effects, interim lab assessments as indicated (aspartate transaminase [AST], alanine transaminase [ALT], urine pregnancy as needed) (Table 2), have vitals and body measurements collected, and be evaluated for depression using the Hamilton Rating Scale for Depression (HAM-D) test. As detailed in the Statistical Analysis section, using a two-sided test at the 0.05 level and anticipating a conservative 90% retention rate, a sample size of 150 participants will provide 90% power to detect significant changes in our primary and key secondary outcomes. Specifics of the above procedures are outlined below.

We will aim to schedule study visits within 8 weeks of the target visit time, but it is possible that the actual visit will be outside of this window. If the final visit is delayed, we may ask the participant to remain on the study medication for no more than 6 additional months based on statistical analysis, resources, funding, or other factors. This will ensure the study team to collect accurate results at the participant's final biomarker visit.

If the participant does not bring their remaining study medication to their final visit, we will provide them with a postage-paid envelope to return the medication to the study team for disposal. If this envelope was not provided at the visit, it will be sent with a letter requesting the return of the study medication. If we do not receive the remaining study medication, the study team will create a note to file documenting that the participant completed the study, but any remaining study medication was not returned.

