#### **Laboratory Evaluation**

Blood samples will be collected after an overnight fast. At baseline and months 9 and 18 (key outcome visits), fasting lipid profiles, glucose, AST, ALT, hs-CRP, and creatinine will be measured using standard enzymatic techniques at the Madison VA Clinical Laboratory. APOE genotyping will be determined from coded specimens by resources from the UW ADRC, the UW Biotechnology Center and/or LGC genomics for a fee for service. Genotyping will occur for all participants at the end of the study using blood samples collected and stored from the pre-study visit. This APOE genotype information will be used in analysis. Baseline analysis of CSF samples will be performed at the WI Alzheimer's Disease Research Center - Biospecimen Lab. This analysis will be for specific measures of beta-amyloid and tau. The UW Biospecimen laboratory will not receive any identifiable information on the research participants as the CSF samples will be coded with their unique subject ID and date, and they will not have access to the key. Coded biospecimen data, including DNA samples will be analyzed to determine various SNP (singlenucleotide polymorphism) sequences. CSF Aβ42, Aβ40, T-tau, and p-tau-181 will be measured with Roche elecsys in the UW ADRC Biomarker Laboratory. Pre- and post-therapy samples will all be run simultaneously at the conclusion of the study to reduce laboratory variability. All biospecimen data will be stored in a freezer, within the secured Madison VA's Research Freezer until clinical analyses occur. Access to the freezer is protected by VA access control, and equipped with backup power and a telephone alarm system. The research freezer space can only be accessed by authorized personnel. Participants will be asked for permission to store their blood, DNA and CSF samples for future research purposes, this will be optional. Samples will be stored for banking purposes specified in the BRAVE Repository Protocol (IRB 2017-0013) and used with consistent approval of the banking repository protocol. Samples will be coded. Specifically, vials containing samples will be labeled with subject ID numbers (###). The label will also include the study name, collection site number, study visit number, contents of each collection vial, and the date of collection. Participants will be made aware, through informed consent, that their samples will be stored for future use.

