The outcomes - rCBF and CSF Aβ42 – were seen to be right skewed based on pilot data; thus, analyses for each specific aim will be conducted on the logarithmic scale so that "mean" refers to the geometric mean outcome. Specific Aim 1 (IPE effects on rCBF) will be addressed with an analysis of covariance on all subjects with 18 month rCBF of the sROI as the outcome, IPE use as a factor, and baseline rCBF as a continuous predictor, with the main hypothesis tested using the coefficient of IPE's effect on mean rCBF. Baseline rCBF is included as a flexible generalization of modeling change in rCBF. The models for Aim 2 (IPE effects on CSF) will take the same form as in Aim 1 except that the endpoints will be CSF AB42 and that we expect the coefficients of IPE to be negative if the alternative hypotheses are true. For exploratory and descriptive purposes, joint longitudinal analyses of baseline, 9, and 18-month outcomes will be conducted using the same model formulations as above and the method of Laird and Ware. Aim 3 is exploratory and will investigate the impact of IPE on 18-month cognitive performance using the constructs proposed for CBF and CSF analyses. The composite ADCS-PACC scores allow for assessment of overall cognitive functioning and a higher level of reliability than is possible with any given individual measure. A linear regression model will be fitted to the raw scores using age, gender, and education as covariates. Using the regression coefficients from this analysis we will calculate predicted scores for each experimental and control subject. The difference between the predicted and observed scores will then be determined for each subject. Relevant statistical graphics will be used to examine all scientific questions.

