#### **Power Calculations**

For Aim 1, using ASL-MRI CBF data from our team's longitudinal WRAP cohort of adults at risk for AD (n=133, ages 43–73) and an interventional statin pilot study of similarly aged adults,16 we anticipate that CBF in the statistical ROI will decline by 15% in the placebo group and 5% in the treatment group over 18 months. With an effect size of 0.57 and a two-tailed  $\alpha$ =0.05, 134 participants (67 per arm) will provide 90% power (1- $\beta$ ) to detect a difference between the two treatment groups. With a conservative 10% drop-out rate (our prior 9-18-month studies with n=88–100 had 94–95% retention rates), 150 participants (presumed 134 [90%] retained at month 18) should provide 90% power to detect a statistically significant difference. Using our team's preliminary baseline data from the SHARP study (Table 1), for Aim 2 we use a baseline CSF A $\beta$ 42 mean  $\pm$  SD of 778.2 $\pm$ 173.2 ng/L (INNOTEST) and a projected IPE-induced decline of approximately 13% in the treatment group and 0% in the placebo group over 18 months. With an effect size of 0.59 and a two-tailed  $\alpha$ =0.05, 124 participants (62 per arm) will provide 90% power (1- $\beta$ ) to detect group differences in CSF biomarkers. As the ADCS-PACC battery (Aim 3) has been principally used in cognitively-healthy, preclinical older adults in their 70s-80s, Aim 3 will be used to understand the performance of this established preclinical cognitive battery in a middle-

aged cohort and to correlate cognitive changes with those noted in primary MRI and CSF biomarker changes.

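### Aim 2 presets an IPE-related fall in CSF Aβ42 as benefit without a stated rationale, and Aβ42 alone cannot show why it fell; Aβ40 is assayed but has no specified analysis

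*Combined protocol and SAP*

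**What the plan says.** **Direction.** The Trial Design Summary hypothesises that "IPE will beneficially affect mechanisms central to AD pathology by" a list of changes, the second of which is lower CSF Aβ42. Under Analyses, Aim 2 is a baseline-adjusted analysis of covariance of 18-month log CSF Aβ42, for which "we expect the coefficients of IPE to be negative if the alternative hypotheses are true". Power Calculations assumes "a projected IPE-induced decline of approximately 13% in the treatment group and 0% in the placebo group over 18 months". The test is two-sided: the Trial Design Summary describes "using a two-sided test at the 0.05 level", and Power Calculations repeats a two-tailed 0.05. Specific Aim (b) is neutral: it asks only what effect IPE has on the CSF markers.

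**Meaning of the level.** Background and Significance counts participants who "have CSF β-amyloid-42 (Aβ42) or tau biomarker levels suggesting preclinical disease", but does not say whether high or low Aβ42 is the abnormal finding. No section explains why a fall would be beneficial.

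**Other CSF markers.** Laboratory Evaluation states that "CSF Aβ42, Aβ40, T-tau, and p-tau-181 will be measured with Roche elecsys in the UW ADRC Biomarker Laboratory", and Table 2 also lists Aβ40. Aβ40 is named in no aim, endpoint, model or power statement, and no Aβ42/Aβ40 ratio is defined. Its only possible place is the open-ended group of further CSF measures among the exploratory analyses. Total tau and p-tau are secondary endpoints under Specific Aims but exploratory in the Trial Design Summary. No rule links them to the reading of Aim 2.

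**The concern.** The Aim 2 endpoint is one concentration, and the plan attaches a favourable meaning to one direction of change. CSF Aβ42 can fall because less peptide is produced or because more of it is retained in plaques. The first would fit the trial's hypothesis; the second would point the other way. This is general subject knowledge that the documents do not state. The Project Summary does say that AD pathology, with amyloid plaques among its features, begins decades before symptoms. Deposition during the trial is therefore conceivable in cognitively healthy Veterans aged 50 to 75.

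Randomisation protects the estimate of the treatment difference. It does not tell the reader what a difference means. If IPE lowers Aβ42 relative to placebo, the plan's wording leads to a report of benefit, and the marker best placed to qualify that report has no assigned analysis although it is measured on the same samples.

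**Working it through.** **1. Reproduce the plan's Aim 2 figure.** Inputs from Power Calculations: baseline mean 778.2 and SD 173.2 ng/L, a 13% fall against 0%, effect size 0.59, two-tailed 0.05, 90% power, 62 per arm.
- Fall: 0.13 × 778.2 = 101.2 ng/L, so 778.2 × 0.87 = 677.0 ng/L.
- Effect size: 101.2 / 173.2 = 0.584. The stated 0.59 corresponds to 0.59 × 173.2 / 778.2 = 13.1%, consistent with a fall of approximately 13%.
- Two-sample t-test at d = 0.59: 61.35, so 62 per arm (124 in total), with power 90.3%.

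The stated figure reproduces. A one-sided calculation would give 50 per arm, so it is indeed two-sided.

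**2. Put the effect on the planned log scale.**
- Log SD = √ln(1 + (173.2/778.2)²) = 0.220.
- Log effect = ln(0.87) = -0.139.
- d = 0.139 / 0.220 = 0.63, giving power 93.8% at 62 per arm without baseline adjustment.

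**3. Compare two patterns with the same Aβ42 fall.** The Aβ40 changes below are assumptions chosen to illustrate the two explanations. The contrast in the ratio follows from them by construction.

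| Assumed pattern | Aβ42 multiplier | Aβ40 multiplier | Aim 2 coefficient | Ratio multiplier | Log ratio |
|---|---|---|---|---|---|
| Lower production | 0.87 | 0.87 | -0.139 | 0.87/0.87 = 1.00 | 0 |
| More Aβ42 retention | 0.87 | 1.00 | -0.139 | 0.87/1.00 = 0.87 | -0.139 |

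The Aim 2 model sees only the Aβ42 column, so its expected coefficient and its power are the same in both rows. The ratio differs.

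**4. Could the ratio be estimated usefully at this sample size?** The documents give neither an SD for Aβ40 nor its correlation ρ with Aβ42. Assume the same log SD (0.220) for both, 62 per arm and no baseline adjustment. Then SD of the log ratio = 0.220 × √(2(1 − ρ)), and d = 0.139 / that SD.

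| ρ (assumed) | SD of log ratio | d | Power for a 13% fall in the ratio |
|---|---|---|---|
| 0.3 | 0.260 | 0.535 | 84% |
| 0.5 | 0.220 | 0.633 | 94% |
| 0.7 | 0.170 | 0.818 | 99.5% |
| 0.9 | 0.098 | 1.416 | over 99.9% |

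If Aβ40 falls in the same proportion as Aβ42, the ratio does not change and the rejection rate stays at 5%. One limit applies throughout: the SD of 173.2 comes from INNOTEST, whereas the trial will use Roche Elecsys, so it may not carry over.

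**5. Why not a pass/fail rule on the ratio?** Suppose benefit required that the point estimate of the ratio not fall and that of p-tau181 not rise. Under a pure production effect the true ratio change is zero, so its estimate falls about half the time. If p-tau181 also has no true change and is independent (an assumption), only 0.5 × 0.5 = 25% of such trials would pass. Requiring non-significance instead would treat lack of evidence as evidence of no change.

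**The case against.** The strongest reply has four parts.

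- **The premise is external.** The documents do not say that low Aβ42 is abnormal, that a fall reflects plaque retention, or that Aβ40 is spared by it. A reader might infer that the protocol contradicts its own background section. It does not, because that section gives no direction. The text also refers to a Preliminary Studies section and a Table 1 that are not in the material available, and a rationale may be there. This stands: what is shown is an unexplained direction, not an internal contradiction.
- **The comparison is randomised, two-sided and baseline-adjusted.** A reader might infer that any decline in Aβ42 will be called benefit. Decline common to both arms cancels, so only an excess fall on IPE is ambiguous. This stands and narrows the point.
- **No decision hangs on Aβ42 alone.** A reader might infer that a rise would be declared a failure, or that a fall would by itself launch larger trials. Neither rule exists. Further trials are tied to beneficial change in AD biomarkers generally, the primary endpoint is rCBF, and Analysis Population says the clinical consequences of these biomarker changes are not clearly known. This stands.
- **Other markers are planned.** Tau, p-tau, NFL, sAPP-α and sAPP-β are to be studied, and Aβ40 could fall under the unspecified exploratory measures. It is therefore too strong to say that Aβ40 will go unused or that the trial as a whole cannot separate the explanations. What remains is that no analysis of Aβ40 is specified and nothing says how any of these markers bears on Aim 2.

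None of this supplies a reason for the direction or a way to read an excess fall.

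**Conclusion.** The point holds as a defect of interpretation on a key secondary endpoint, and it should be fixed. The plan assigns a beneficial meaning to an IPE-related fall in CSF Aβ42 without saying why. Its Aβ42-only model would give an expected coefficient of -0.139 for a 13% fall whichever of the two explanations were true. The Aβ42 test remains valid, the 62 per arm reproduces, and rCBF is untouched.

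A reader might go further and conclude that the trial would report the wrong sign. The documents do not support that: they give no basis for the probability of either explanation, and this review estimates none. The conclusion rests on general subject knowledge about why CSF Aβ42 falls. The claim that the ratio could be estimated with useful power rests on the assumed Aβ40 variance and correlation, and on the INNOTEST SD carrying over to Elecsys.

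**What to change.** 1. Keep the two-sided Aβ42 analysis as the Aim 2 test.
2. Prespecify 18-month log(Aβ42/Aβ40), adjusted for its own baseline and fitted in the same model form, as a companion analysis. Report Aβ40 and p-tau181 alongside.
3. State the rationale for expecting a fall in Aβ42 to be beneficial.
4. Replace the unconditional benefit wording in the Trial Design Summary, and the matching expectation under Analyses, with a statement that an Aβ42 fall is interpreted together with the ratio estimate and its confidence interval. A fall in both is reported as not distinguishable from increased deposition.
5. Do not use a pass/fail gate on point estimates or on non-significance.
6. Reconcile Specific Aims with the Trial Design Summary on whether tau and p-tau are secondary or exploratory.

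Laboratory Evaluation says pre- and post-therapy samples are run together at the end of the study, so the rule can be fixed before those results exist. Part of the Specific Aims text describes the rCBF analysis in the past tense. If CSF results by arm have already been seen, the companion analysis must be labelled post hoc.

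**Cost.** Protocol and SAP wording and one more secondary analysis; no new assay is needed. A fall in Aβ42 alone would no longer support a claim of benefit.

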#### **Specific Aims:**

- (a) To investigate the effects of 18 months of IPE 4 g daily vs. placebo on arterial spin-labeling (ASL) MRI regional cerebral blood flow (rCBF) in a pre-defined statistically-identified region of interest (ROI) affected early in preclinical AD.
- **(b)** To determine the impact of 18 months of IPE vs. placebo on CSF biomarkers of preclinical AD pathology (CSF  $\beta$ -amyloid-42, total tau, and phosphorylated tau181).

**(c)** To evaluate the effects of 18 months of icosapent ethyl vs. placebo on a composite measure designed to assess preclinical cognitive changes — the Alzheimer's Disease Cooperative Study (ADCS) Preclinical Alzheimer's Cognitive Composite (PACC).

Description of the primary endpoint: The primary endpoint will be the change in rCBF in a predefined statistical ROI at 18 months in participants randomized to IPE vs. placebo. Animal and human studies show that regionally reduced CBF (related to both neuronal hypometabolism and systemic vascular disease) in areas of the brain important for memory and learning is a very early change in AD pathogenesis and, thus, therapies known to beneficially modify arterial function may improve CBF and lead to early neuroprotection and maintenance of cognitive function. The predefined statistical ROI that will be used for the proposed trial was developed using longitudinal ASL-MRI CBF data from 133 adults (ages 43-73) in the NIH-funded Wisconsin Registry for Alzheimer's Prevention (WRAP) cohort, which is enriched for parental history of AD. Areas of the brain with greatest CBF decline over two years were identified using the Alzheimer's Disease Neuroimaging Initiative (ADNI)-derived analytic method developed by Chen et al. The statisticallydefined region is consistent with those affected early by AD pathology. Using anatomical ROIs that aligned with the statistically-defined ROI, treatment effect on 18 month rCBF was examined hierarchically in a priori selected regions of interest in the following order: bilateral posterior cingulate, bilateral precuneus, bilateral medial temporal lobe. Analyses of ROIs were discontinued if the group difference in 18 month rCBF in the previous ROI was not significant. Secondary endpoints will be 18-month changes in CSF biomarkers of AD pathology (Aβ42, t-tau, p-tau) and changes in ADCS-PACC cognitive score.

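### The 90% power claimed for key secondary outcomes has no calculation behind it for ADCS-PACC, and the PACC treatment comparison is not fixed to one model

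*Combined protocol and SAP*

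**What the plan says.** **Power and status.** The Trial Design Summary states that "a sample size of 150 participants will provide 90% power to detect significant changes in our primary and key secondary outcomes", and refers to the statistical section for detail. The same section lists three aims and places Aim 3, "to assess whether IPE improves cognitive performance on the ADCS-PACC battery compared to placebo", among the key secondary ones. The Specific Aims section lists the secondary endpoints as the CSF biomarkers "and changes in ADCS-PACC cognitive score". The Power Calculations section gives an effect size and sample size for Aim 1 (rCBF) and Aim 2 (CSF Aβ42). For cognition it says only that "Aim 3 will be used to understand the performance of this established preclinical cognitive battery" in a middle-aged cohort, and that cognitive changes will be correlated with the biomarker changes.

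**Analysis.** The Analyses section notes right skew in rCBF and CSF Aβ42 and concludes: "thus, analyses for each specific aim will be conducted on the logarithmic scale". On cognition it says: "Aim 3 is exploratory and will investigate the impact of IPE on 18-month cognitive performance using the constructs proposed for CBF and CSF analyses". Those constructs are an analysis of covariance of the month-18 value with a treatment factor and the baseline value as a continuous predictor. It then continues: "A linear regression model will be fitted to the raw scores using age, gender, and education as covariates". Predicted scores follow, and the last step is: "The difference between the predicted and observed scores will then be determined for each subject".

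The cognitive battery paragraph under Laboratory Evaluation describes something else: a between-arm comparison of change in the composite, adjusted for practice effects by a method it does not give. There the composite is the sum of four component change scores, each divided by that component's baseline SD. The Covariates section requires all cognitive analyses to be adjusted for age, sex and education.

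**The concern.** Two things do not fit together.

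First, PACC is a key secondary aim covered by a 90% power statement in one place, and an exploratory aim with no power calculation in another. A null PACC result could then be read against a power figure that was never worked out for it.

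Second, the PACC analysis appears in several forms, and the plan does not say which one is the analysis. The log scale cannot be applied to a signed sum of changes. The regression that is written out names no treatment term and no baseline term, and ends before any comparison of the arms. A between-arm comparison is clearly intended, but the analyst would have to choose between change scores, month-18 analysis of covariance and demographic residuals once the data are in. Any one of these would be a valid comparison by itself. What is at stake is precision, and a treatment analysis of the trial's cognitive endpoint that is not fixed in advance.

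**Working it through.** **1. The plan's own power figures.** Two-sample comparison of means, two-sided 0.05, 1:1 allocation, noncentral t; inputs from Power Calculations.

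| Aim | Effect size | Per arm | Stated power | Recomputed |
|---|---|---|---|---|
| 1 (rCBF) | 0.57 | 67 | 90% | 90.6% |
| 2 (CSF Aβ42) | 0.59 | 62 | 90% | 90.3% |
| 3 (ADCS-PACC) | none | none | none | cannot be computed |

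The total also reproduces: 134 / 0.9 = 148.9, and the plan uses 150. Aims 1 and 2 are not in dispute. For PACC the documents give no effect size, SD, correlation or sample size.

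**2. What 67 per arm can detect on PACC, using the same two-sample convention.** The detectable difference is 0.564 SD at 90% power and 0.488 SD at 80%. For assumed true differences of 0.2, 0.3 and 0.4 SD, power is 0.209, 0.407 and 0.632.

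**3. How much the choice of form matters.** Let ρ be the correlation between the baseline and month-18 composites. It is not in the documents, so 0.6, 0.7 and 0.8 are assumed. Demographics are assumed to explain 20% of the variance. With the month-18 variance set to 1, the variance entering the treatment comparison is:

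- analysis of covariance on baseline: 1 − ρ²
- change score, no baseline covariate: 2(1 − ρ), which relative to the line above is 2/(1 + ρ)
- month-18 score adjusted for demographics only: 0.80, a ratio of 0.80/(1 − ρ²)

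Take an effect that has 80% power under the first form:

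| ρ | Ratio, change score | Power | Ratio, month-18 without baseline | Power |
|---|---|---|---|---|
| 0.6 | 1.25 | 0.707 | 1.25 | 0.707 |
| 0.7 | 1.18 | 0.733 | 1.57 | 0.609 |
| 0.8 | 1.11 | 0.757 | 2.22 | 0.468 |

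If the covariance model also includes the demographics (equal slopes at both visits assumed), its residual variance is 0.8(1 − r²) with r = (ρ − 0.2)/0.8, that is 0.600, 0.4875 and 0.350. The comparison powers become 0.679, 0.714 and 0.746 for change scores, and 0.679, 0.590 and 0.457 for month-18 scores without baseline. The 90% detectable difference for this model is 0.564 × √0.600 = 0.44, 0.564 × √0.4875 = 0.39 and 0.564 × √0.350 = 0.33 of the month-18 SD.

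**4. Simulation check.** With 67 per arm, a true difference of 0.3 SD and 20% of variance from demographics, comparing month-18 residuals without baseline gave 47% to 48% power. The model with treatment, demographics and baseline gave 53%, 68% and 82% at ρ = 0.5, 0.7 and 0.8. With no true effect, rejection rates lay between 4.45% and 5.55% for both, so type I error of either single form is not the problem.

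**5. The log scale.** With an assumed mean change of 0 to 0.2 SD per component, ρ from 0.5 to 0.8 and a correlation of 0.3 between component changes, about 32% to 50% of change composites are zero or negative. Their logarithm does not exist.

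**6. Change or month-18 outcome.** A composite built from change scores is zero for everyone at baseline, so it cannot serve as its own baseline covariate. If a level composite is formed at each visit by standardising the components to the baseline mean and SD and summing, the means cancel in the difference. Month-18 minus baseline is then exactly the change composite in the cognitive battery paragraph. With the baseline composite in the model, either outcome gives the same treatment coefficient. On simulated four-component data (n = 134) it was 0.9493 with SE 0.1709 both ways.

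**The case against.** The strongest reply is that the plan already treats cognition as exploratory and gives a reason: the battery has mainly been used in adults in their 70s and 80s. The power sentence sends the reader to the statistical section, where 90% is attached to Aims 1 and 2 only. On the model, the log sentence opens with rCBF and CSF Aβ42, and the text then specifies raw scores for PACC. The paragraph can also be read in sequence: adjust for demographics, take residuals, then apply the Aim 1 constructs with treatment and baseline. On that reading the change and month-18 forms coincide, and the larger power losses, which require dropping baseline, do not arise. The correlations and the demographic share of variance are assumptions.

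Part of this stands. The log sentence is probably loose wording, the reference to the Aim 1 constructs does point towards a baseline-adjusted comparison, and the loss to 47% occurs only if baseline is left out altogether. It does not remove the point. The power sentence covers PACC as long as Aim 3 is a key secondary aim, and the section it cites does not support that. The favourable reading of the model has to be assembled by the reader: nothing says that the residuals enter the Aim 1 model, at which visit the regression is fitted, or how the separately described comparison of changes relates to it. The exploratory label is a reason to correct the power sentence and the endpoint list; it does not reconcile them.

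**Conclusion.** The concern holds. The 90% power statement has no basis for ADCS-PACC. Using the plan's own two-sample convention at 67 per arm, it would require a true difference of about 0.56 SD; differences of 0.2 to 0.4 SD have 21% to 63% power. The PACC analysis is described in forms that cannot all be the analysis. If baseline adjustment is not used, an effect with 80% power under it falls to 71–76% with change scores, or to between 71% and 47% with month-18 scores alone. These losses rest on assumed correlations of 0.6 to 0.8 and, for the month-18 form, 20% of variance explained by demographics. The primary endpoint, the Aim 1 and 2 power figures and the sample size are unaffected. This should be corrected, but it does not threaten the main inference.

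**What to change.** 1. In the Trial Design Summary, limit the 90% power statement to Aims 1 and 2. Alternatively, state the detectable PACC difference: about 0.56 SD unadjusted at 67 per arm. If a baseline-adjusted figure is quoted instead (0.33 to 0.44 SD under the assumptions above), state the correlation and demographic variance it assumes.
2. Give Aim 3 one status in Specific Aims, Trial Design Summary and Analyses. Exploratory is the status that the Analyses and Power Calculations sections support.
3. In Analyses, limit the log scale to rCBF and CSF Aβ42.
4. In Analyses, replace the predicted-versus-observed step with one untransformed linear model: month-18 PACC composite on treatment, baseline PACC composite, age, sex and education, testing the treatment coefficient. This keeps the Aim 1 form and the required covariates.
5. In the cognitive battery paragraph, define the baseline and month-18 composites as component scores standardised by the baseline mean and SD, then summed. State that the change composite is their difference and gives the same treatment coefficient in this model, and that practice effects are handled by the concurrent placebo comparison.

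The cost is protocol and SAP wording, with no new data or procedures. The one drawback for the sponsor is a narrower power statement.
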